9.1 Efficacy and/or Immunogenicity Assessments

Not applicable.

9.2 Safety Assessments

Safety will be assessed through incidence of TEAEs, including infusion-related and local infusion-site reactions, electrocardiograms (ECGs), clinical laboratory evaluations (including haematology, blood chemistry and urinalysis), vital signs, and physical examination findings.

Any clinically significant observations, as determined by the Investigator, in results of clinical laboratory, 12-lead ECGs, vital signs, or physical examinations will be recorded as AEs.

Planned timepoints for all safety assessments are provided in the SoA (see [Table 1](#) and [Table 2](#)).

9.2.1 Adverse Events, Serious Adverse Events, and Other Safety Reporting

The definitions of AEs and serious AEs (SAEs) can be found in [Appendix 3](#).

The subject/subject's parent(s)/LAR, or a caregiver will be asked in general terms about any AEs at regular intervals during the study. In addition, all AEs reported spontaneously by the subject/subject's parent(s)/LAR, or a caregiver during the course of the study will be recorded.

The Investigator and any qualified designees are responsible for detecting, documenting, and recording events that meet the definition of an AE or SAE and remain responsible for following up until resolution, all AEs that are serious, considered related to the study treatment or that caused the subject to discontinue the study treatment.

The method of recording, evaluating, and assessing causality of AEs and SAEs and the procedures for completing and transmitting SAE reports are provided in [Appendix 3](#).

9.2.2 Time Period and Frequency for Collecting AE and SAE Information

All AEs/SAEs will be collected from the start of IV infusion until the Follow-up visit at the timepoints specified in the SoA (see [Table 1](#) and [Table 2](#)).

Medical occurrences that begin before the start of study treatment but after obtaining informed consent will be recorded as medical history/current medical conditions, not as AEs.

All SAEs will be recorded and reported to the Sponsor or designee immediately and under no circumstance should this exceed 24 hours from the time of awareness, as indicated in [Appendix 3](#). The Investigator will submit any updated SAE data to the Sponsor within 24 hours of it being available.

Investigators are not obligated to actively seek information on AEs or SAEs after conclusion of the study participation. However, if the Investigator learns of any SAE, including a death, at any time after a subject has been discharged from the study, and he/she considers the event to be reasonably related to the study treatment or study participation, the Investigator must promptly notify the Sponsor.

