5.1.5 Follow-up or Early Termination

The Follow-up assessments will be performed on Day 30 (\pm 5 days) for all subjects. In case of subjects who withdraw consent before the Follow-up visit, or are discontinued early (for safety reasons) from the study, early termination (ET) assessments can be performed at the time of discontinuation. The reason for ET must be recorded in the eCRF. In cases where a subject is discontinued before all PK samples have been collected, a last PK sample can be collected if the subject and/or his/her parent(s)/LAR consents. The exact date and time of the PK sample must be recorded.

The following assessments will be performed at Follow-up or ET:

- Record concomitant medication use (includes medications that are ongoing or started after Day 1)
- Complete physical examination: A complete physical examination will include, at a minimum, assessments of the cardiovascular, respiratory, gastrointestinal, and central and peripheral neurological system
- Vital signs: Vital signs will be taken after subject is sitting or supine for at least 5 minutes and will include temperature, pulse rate, respiratory rate, and blood pressure
- Clinical laboratory tests: haematology, biochemistry and urinalysis (see Appendix 2 for details)
- Urine pregnancy test (for postmenarcheal females)
- Record TEAEs/SAEs (see Appendix 3)
- For ET, in addition to the above, reason for early termination must be recorded in the eCRF

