8 DISCONTINUATION OF STUDY TREATMENT AND SUBJECT DISCONTINUATION/ WITHDRAWAL

8.1 Discontinuation of Study Treatment

This is a single-dose study. All subjects enrolled will receive a single infusion of IP (rezafungin).

Stopping Rules

Stopping Criteria for an Individual Subject

- In case of any systemic reaction (i.e., cytokine release syndrome, including nausea, headache, tachycardia, hypotension, rash, and/or shortness of breath) or local infusion-related reaction (i.e., injection site pain or tenderness, erythema or redness, induration or swelling, or pruritis) with a severity of Grade 2 or higher (according to the DAIDS criteria, Version 2.1), the infusion will be immediately stopped and not restarted, and treatment provided as appropriate. The date and time of discontinuation must be recorded in the eCRF. The Sponsor/medical monitor must be informed immediately (no later than 24 hours of Principal Investigator's knowledge of the event). Where feasible, the PK assessment will continue if the subject is well enough and willing to continue.
Note: in case of Grade 1 local reactions, the investigator may slow down the infusion or temporarily discontinue the infusion (see Section 7.6).
- A subject becomes pregnant.

Criteria for Pausing or Stopping the Study

The study would be paused in cases where:

- One subject experiences a serious unexpected adverse event that is considered at least possibly related to rezafungin. The event will be investigated and the causality established before dosing the next available subject.

The study would be stopped in cases where any of the following occurs:

- A study drug-related significant adverse reaction (i.e., a serious AE considered at least possibly related to the IP administration) leading to treatment discontinuation in 2 subjects
- Two or more subjects have experienced a Grade ≥ 4 AE considered to be related to rezafungin
- The Investigator and the Sponsor both agree that the tolerability profile is unacceptable, based on the frequency and intensity of observed AEs (including serious and related AEs)
- At the request of the DSMB, based on a safety concern during the review of the safety and tolerability data

- Additional data from other clinical trials or toxicological studies become available that negatively influence the risk/benefit assessment
- At a specific site/in a specific region: if the local regulatory authority or Independent Ethics Committee (IEC) withdraws approval of the study

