8.2 Subject Discontinuation/Withdrawal from the Study

Participation in the study is strictly voluntary.

- A subject has the right to withdraw from the study at any time for any reason.
- The subject's parent(s)/LAR (as applicable) may choose to withdraw the subject from the study at any time or the subject may be withdrawn at any time at the discretion of the Investigator for safety (due to AEs or SAEs), or compliance reasons.
- At the time of discontinuation from the study, if possible, an ET visit should be conducted, as shown in the SoA. For data to be collected at the time of study discontinuation see SoA ([Table 1](#) and [Table 2](#)). The subject will be permanently discontinued from the study treatment and the study at that time.
- If the subject or subject's parent(s)/LAR withdraws consent for disclosure of future information, the Sponsor may retain and continue to use any data collected before such a withdrawal of consent.
- If a subject withdraws from the study, he/she or the subject's parent(s)/LAR may request destruction of any samples taken and not tested, and the Investigator must document this in the source documents and relevant medical records. Samples not yet tested at the time of destruction request will be destroyed.
- The reason for withdrawal will be recorded in the eCRF.

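### A dosed subject who leaves early but can still be contacted has no active, scheduled collection of new adverse events between early termination and Day 30 (minor; cheap to improve)

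*Combined protocol and SAP*

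**What the plan says.** Section 9.2.2 collects AEs and SAEs from the start of the infusion to the Follow-up visit, at the times in the Schedule of Assessments. Follow-up is on Day 30 (± 5).

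For early leavers, section 8.2 allows a subject or parent to withdraw, and a subject may also be "withdrawn at any time at the discretion of the Investigator for safety (due to AEs or SAEs), or compliance reasons". It continues: "At the time of discontinuation from the study, if possible, an ET visit should be conducted, as shown in the SoA". And then: "The subject will be permanently discontinued from the study treatment and the study at that time".

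In Tables 1 and 2, Follow-up and ET share one column. Section 5.1.5 gives them a single list of procedures, introduced by "The following assessments will be performed at Follow-up or ET", which includes recording TEAEs and SAEs. Its wording on whether ET assessments take place is permissive.

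Once participation is over, section 9.2.2 states: "Investigators are not obligated to actively seek information on AEs or SAEs after conclusion of the study participation". The exception applies "if the Investigator learns of any SAE, including a death, at any time after a subject has been discharged from the study" and considers it reasonably related to treatment or participation; the sponsor must then be told promptly.

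**The concern.** Taken together, these sections let active AE collection stop at ET for a subject who has been dosed and can still be reached. That subject remains in the Safety Analysis Set, which includes everyone who received any rezafungin (10.3). The synopsis counts TEAEs up to the Follow-up, and section 10.4.5 reports numbers and percentages of subjects by group. The available text makes no allowance for a shorter observation period. A leaver with no AE before ET is counted as event-free, even if an event begins the following week and nobody asks.

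Safety is the secondary objective, and the groups are of about 8. The first DSMB review waits until all of Group 1 have completed Follow-up (5.1, 10.6), so the design itself treats safety data out to Day 30 as relevant before younger children are dosed. Early exits are also foreseen: subjects withdrawn before completing PK sampling may be replaced, up to 2 per group.

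**Working it through.** The plan states no figure on this point, so there is nothing to reproduce. The check is of the text, followed by arithmetic that only bounds the effect.

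**Does any provision actively collect new AEs after ET?**

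- 9.2.2, collection until Follow-up: tied to scheduled timepoints. After ET the leaver has none.
- 9.2.1: site staff "remain responsible for following up until resolution, all AEs that are serious, considered related to the study treatment", or that led to stopping treatment. This concerns events already identified.
- 9.2.3 and Appendix 3 (follow-up of AEs and SAEs): proactive, and continuing after the follow-up visit, but triggered by an event already reported. Such contact may bring a new event to light; it is not planned for that purpose.
- 9.2.2, SAEs after discharge: passive, and limited to SAEs that the investigator hears of and considers related.
- Appendix 3 (unsolicited AEs): families are told to contact the site about medically attended events and others that concern them. No end date is stated. Passive, and not expressly extended past ET.
- 8.3: telephone calls and a letter after a missed visit, to learn whether the subject will continue. Not AE collection after ET.

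None is an active, scheduled contact for new AEs between ET and Day 30.

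**Who is affected?** Section 8.2 treats withdrawing consent to disclose future information as a separate step from leaving, so some leavers may remain reachable. Those withdrawn for a post-dose AE already count under any TEAE and can lose only further preferred-term, severity, SAE or AESI counts. For the any-TEAE row, the exposed subjects are reachable leavers with no earlier TEAE.

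**Bound on the tables.** If m leavers have an uncaptured event not already counted in a row, the row falls by m/n. With m = 1:

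- per group: 1/8 = 12.5 points; 1/10 = 10.0 points (the maximum group size)
- overall: 1/32 = 3.1 points; 1/40 = 2.5 points

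The documents give no value for m, and it may be 0.

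**Part of the AE window without scheduled collection.** With dosing on Day 1, ET on Day E and Follow-up on Day F, the share is (F − E)/(F − 1). The ET days are illustrative.

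| ET day | F = 25 | F = 30 | F = 35 |
|---|---|---|---|
| 3 | 22/24 = 91.7% | 27/29 = 93.1% | 32/34 = 94.1% |
| 8 | 17/24 = 70.8% | 22/29 = 75.9% | 27/34 = 79.4% |

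**Drug still present.** Section 3.3 gives an adult half-life h of around 5 to 6 days. The fraction left on Day d is at most about 2^(−(d − 1)/h):

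- Day 3: 2^(−2/5) = 75.8%; 2^(−2/6) = 79.4%
- Day 8: 2^(−7/5) = 37.9%; 2^(−7/6) = 44.5%
- Day 30: 2^(−29/5) = 1.8%; 2^(−29/6) = 3.5%

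These are upper bounds because the model in 5.3 has three compartments and the terminal phase is the slowest. Applying the adult half-life to children is an assumption. The figures show that exposure may continue after an early exit; they say nothing about how often AEs occur.

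**The case against.** The strongest reply is that very few subjects are exposed. Many voluntary withdrawals end contact altogether. A subject withdrawn for safety already has an event, and 9.2.3 then asks for proactive follow-up of the subject, not only of the event. Non-compliance after one supervised infusion mostly means missed visits, which prompt the contact attempts in 8.3. Recruitment is from hospital inpatients, so the site may see later events in routine care. This stands: it limits the size and keeps the point minor. It does not supply a planned contact for the reachable leaver.

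A second reply is that collection until Follow-up, and Follow-up on Day 30 for all subjects (5.1.5), already cover leavers. The wording can be read so, but discontinuation from the study at exit and the shared Follow-up/ET column leave no procedure for doing it.

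A third is that the analysis detail belongs in the SAP, which section 10 says will be finalised before database lock. That is fair for the reporting part, and its absence here is not evidence that it was omitted. No SAP can recover events that were never collected.

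A reader might also infer more than the documents support:

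- *Stopping the infusion ends safety observation.* Section 8.1 says otherwise: "Where feasible, the PK assessment will continue if the subject is well enough and willing to continue".
- *Everything after ET is lost.* The Appendix 3 instruction to families, reporting of related SAEs and follow-up of open events all remain.
- *The neurological examination is lost.* The ET visit includes the same complete examination, only earlier; it is lost only if no ET visit takes place.

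**Conclusion.** The point holds as a cheap improvement, rated minor. Followed as written, sections 5.1.5, 8.2 and 9.2.2 give a dosed, reachable early leaver a shorter active AE window while keeping that subject in the safety denominator. TEAE counts in the descriptive summaries and in the DSMB's safety data may be too low.

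The total size is unknown and may be zero. The 12.5 points is a ceiling for one missed subject in one row of a group of 8, not an expected bias, and the expected loss is smaller if AEs cluster near dosing. The conclusion rests on two assumptions: that some early leavers still permit contact, and that participation ends at exit as 8.2 states. No hypothesis is tested (10.2), and the PK endpoints are not affected. The documents do not support a claim that the safety results are materially biased.

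**What to change.** In 5.1.5 and 8.2, state that, unless consent to follow-up is withdrawn, a dosed subject who leaves early has the ET visit and also a safety visit or telephone contact on Day 30 (± 5), with all new AEs collected until then. Beside the TEAE tables, report for each group the number of subjects whose last AE contact was before Day 25. Stating the cut-off as a study day avoids flagging a completer seen on Day 25, who has 24 elapsed days.

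The cost is protocol wording and about one extra visit or call per reachable early leaver. Nothing is recovered for subjects who withdraw consent to follow-up. The substantial amendment already planned for the paediatric formulation, before Part 2, is a convenient place for the change.

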9.2.3 Follow-up of AEs and SAEs

After the initial AE/SAE report, the Investigator is required to proactively follow up each subject. All SAEs and AEs of special interest (as defined in Section [9.2.6](#)) will be followed up until resolution, stabilisation, the event is otherwise explained, or the subject is lost to follow-up. Further information on follow-up procedures is provided in [Appendix 3](#).

9.2.4 Regulatory Reporting Requirements for SAEs

Prompt notification by the Investigator to the Sponsor of an SAE is essential so that legal obligations and ethical responsibilities towards the safety of subjects and the safety of a study treatment under clinical investigation are met.

The Sponsor has a legal responsibility to notify both the local regulatory authority and other regulatory agencies about the safety of a study treatment under clinical investigation. The

Sponsor will comply with country-specific regulatory requirements relating to safety reporting to the regulatory authority, IECs, and Investigators.

An Investigator who receives an Investigator safety report describing an SAE or other specific safety information (e.g., summary or listing of SAEs) from the Sponsor will review and then file it along with the study documents and will notify the IEC, if appropriate according to local requirements.

Investigator safety reports must be prepared for suspected unexpected serious adverse reactions (SUSARs) according to local regulatory requirements and Sponsor policy and forwarded to Investigators as necessary.

All confirmed (laboratory-tested positive result) and suspected cases of COVID-19 that occur from the signing of informed consent through the Follow-up visit, whether symptomatic or not, will be reported as AEs.

9.2.5 Pregnancy

Details of all pregnancies in female subjects and, if indicated, female partners of male subjects will be collected after the start of study treatment and until the time period for reporting pregnancies (should align with the time period for post-treatment contraception determined in Section 6.1).

If a pregnancy is reported, the Investigator will record pregnancy information on the appropriate form and submit it to the Sponsor within 24 hours of learning of the female subject or female partner of a male subject (after obtaining the necessary signed informed consent from the female partner) pregnancy. All pregnancies will be followed up for the outcome of pregnancy.

While pregnancy itself is not considered to be an AE or SAE, any pregnancy complication or termination of a pregnancy for medical reasons will be reported as an AE or SAE.

Abnormal pregnancy outcomes (e.g., spontaneous abortion, foetal death, stillbirth, congenital anomalies, ectopic pregnancy) are considered SAEs and will be reported as such.

9.2.6 Adverse Event of Special Interest

In addition to SAEs, the following are considered an adverse event of special interest (AESI) and should be promptly reported to the Sponsor within 24 hours of awareness through the Reporting of SAEs process as defined in [Appendix 3](#), even if the nature of the AE is deemed non-serious according to the usual regulatory criteria.

Infusion-related reactions

Events that, in the opinion of the Investigator, may represent intolerance of the IV infusion of the IP. In general, these events would be temporally associated with the IV infusion of the Sponsor's IP.

Phototoxicity

Due to results from a nonclinical phototoxicity study in rats and a Phase 1 clinical trial indicating that rezafungin causes an increased risk for phototoxicity, classified as mild, subjects should be advised to avoid sun and other UV light exposure without adequate protection from Day 1 to Day 8 (i.e., including 7 days after the administration of rezafungin). Investigators should report any AE potentially related to or suspicion of phototoxicity to the Sponsor.

Neurological manifestations (such as ataxia, tremor and neuropathy)

In a rezafungin 3-month toxicity study in monkeys, there were observations of tremors, and histology with Schwann cell hypertrophy/hyperplasia (reversible) and phospholipidosis in the dorsal root ganglia first appearing at Week 6 of dosing and at 9.2-fold the exposure to the dosing regimen of rezafungin used in the Phase 3 pivotal study. Ataxia, axonal neuropathy, hypoesthesia, hyperesthesia, paraesthesia, peripheral neuropathy (motor, sensory, or sensorimotor), polyneuropathy, toxic neuropathy, and tremors will be considered AESIs.

9.2.7 Physical Examination

A complete physical examination is to be performed at Screening and Follow-up. At all other time points, a brief targeted examination is to be performed as clinically indicated, driven by the subject's symptoms and signs. A complete and brief targeted physical examination will include, at a minimum, assessments of the cardiovascular, respiratory, gastrointestinal, and central and peripheral neurological systems.

9.2.8 Vital Signs

Vital signs will be measured in a sitting or supine position after 5 minutes rest and will include temperature, systolic and diastolic blood pressure, pulse, and respiratory rate.

9.2.9 Electrocardiograms

Single 12-lead ECG(s) will be obtained as outlined in the SoA (see [Table 1](#) and [Table 2](#)) using an ECG machine that automatically calculates the heart rate and measures PR, QRS, QT, and QTc intervals. ECGs will be judged by the Investigator for clinical significance.

9.2.10 Clinical Safety Laboratory Tests

See [Appendix 2](#) for the list of clinical laboratory tests to be performed and see [Table 1](#) and [Table 2](#) for the timing and frequency.

The Investigator must review the laboratory report, document this review, and record any clinically significant changes occurring during the study as an AE. The laboratory reports must be filed with the source documents.

Abnormal laboratory findings associated with the underlying disease are not considered clinically significant unless judged by the Investigator to be more severe than expected for the subject's condition.

All laboratory tests with values considered clinically significantly abnormal during participation in the study should be repeated until the values return to normal or baseline or are no longer considered clinically significant by the Investigator or medical monitor.

- If clinically significant values do not return to normal/baseline within a period of time judged reasonable by the Investigator, the aetiology should be identified, and the Sponsor notified.
- All protocol-required laboratory tests, as defined in [Appendix 2](#), must be conducted in accordance with the Laboratory Manual and the SoA ([Table 1](#) and [Table 2](#)).
- If laboratory values from non-protocol-specified laboratory tests performed require a change in subject management or are considered clinically significant by the Investigator then the results must be recorded.

9.3 Pharmacokinetic Assessment

9.3.1 Collection of Blood Samples for Pharmacokinetic Assessment

At the time points defined in the SoA ([Table 1](#)), blood samples of 1 mL each will be collected for the analysis of rezafungin plasma concentration. For subjects from birth to <2 years of age (Group 4; [Table 2](#)), a maximum total of 1 mL of blood will be taken for PK sampling. The blood samples will be taken via an indwelling IV catheter or arterial line or by direct venepuncture. The exact times of blood sampling will be recorded in the eCRF.

The method of PK blood draws is at the discretion of the Investigator (e.g., via indwelling central venous catheter, port-a-cath, arterial line, or peripheral phlebotomies). However, it is advised to avoid taking PK samples from the same catheter used for rezafungin administration, especially for the end-of-infusion timepoint. In subjects with an indwelling central venous catheter or port-a-cath, it is recommended to administer rezafungin via an alternative line (e.g., a peripheral line) and obtain all PK samples via the central venous catheter or port-a-cath. For procedures for taking PK samples from an indwelling catheter, follow the site's standard of care to prevent contamination of PK samples from the dose administered.

Samples collected for analyses of rezafungin plasma concentration may also be used to evaluate safety aspects related to concerns arising during the study.

Details on sample collection, handling, storage, and shipping will be described in the Laboratory Manual.

9.3.2 Pharmacokinetic Assessments for Part 1 and Part 2

Subjects enrolled in Part 1 (aged 12 to <18 years) and Part 2 (aged 2 to <12 years) will undergo PK sampling as described below:

Blood samples will be collected for measurement of plasma rezafungin concentrations at the following 5 timepoints: at end-of-infusion \pm 15 minutes, then between 3 and 4 hours after start of infusion, between 6 and 8 hours after start of infusion, at 48 hours (\pm 4 hours) after start of infusion, and at 168 hours (\pm 12 hours) after start of infusion. The exact time and date of the PK samples must be recorded.

Approximately 5 mL of blood (5 samples, 1 mL each) will be taken from each subject for the measurement of rezafungin concentrations.

9.3.3 Pharmacokinetic Assessments for Part 3

In Part 3, blood samples for measurement of plasma rezafungin concentrations will be collected at the following 3 timepoints: at end-of-infusion \pm 15 minutes, at 24 hours (\pm 4 hours) after start of infusion, and at 168 hours (\pm 12 hours) after start of infusion. The exact date and time of the PK samples must be recorded.

A maximum total of 1 mL of blood (3 samples) will be taken from each of the 8 subjects for the measurement of rezafungin concentrations.

